## List of Abbreviations

ACOG	American College of Obstetricians and Gynecologists
ADA	American Diabetes Association
AE	Adverse Event
BMI	Body Mass Index
BPA	(Epic) Best Practice Alert
CLB	(UPMC) Clinical Laboratory Building
Co-I	Co-Investigator
CRHC	Center for Research on Health Care
CRHC-DC	Center for Research on Health Care – Data Center
CSSD	Computing Services and Systems Development
CTRC	Clinical and Translational Research Center
CTSI	Clinical and Translational Science Institute
DM	Diabetes Mellitus
DOB	Date of Birth
DSMB	Data Safety Monitoring Board ( a.k.a. IDSMB)
EBL	Estimated Blood Loss
ED	Emergency Department
EDC	Estimated Date of Confinement
EHR	Electronic Health Record ( a.k.a. EMR)
EMR	Electronic Medical Record ( a.k.a. EHR)
eSYSDM	Electronic System for Data Management
GA	Gestational Age
GDM	Gestational Diabetes Mellitus
GSPH	Graduate School of Public Health
GCT	Glucose Challenge Test
hsCRP	High-sensitivity C-reactive Peptide
IADPSG	International Association of the Diabetes and Pregnancy Study Groups
ICD	Informed Consent Document
IDSMB	Institutional Data Safety Monitoring Board ( a.k.a. DSMB)
IRB	Institutional Review Board
LDR	Labor and Delivery Room
LGA	Large for Gestational Age
LMP	Last Menstrual Period
LTFU	Lost to Follow-Up
MFM	Maternal-Fetal Medicine
MRN	Medical Record Number
MWH	Magee-Womens Hospital

MWRI	Magee-Womens Research Institute
NICHD	National Institute of Child Health and Human Development
NICU	Neonatal Intensive Care Unit
NIH	National Institutes of Health
OB	Obstetrician/Obstetrics
OGTT	Oral Glucose Tolerance Test
OSPU	Obstetric Specimen Procurement Unit
PI	Principal Investigator
R3	Health Research Records Request
RA	Research Assistant
RC	Research Coordinator
SAE	Serious Adverse Event
SGA	Small for Gestational Age
TOLAC	Trial of Labor After C-section
UPMC	University of Pittsburgh Medical Center

## Study Flow Chart and Randomization Schema

GDM2 Study Timeline (from grant)										
Study Activity/Months	1-6	6-12	12-18	18-24	24-30	30-36	36-42	42-48	48-54	54-60
Orientation & Start-Up	x									
Finalize IRB	x									
Enrollment		x	x	x	x					
Intervention		x	x	x	x	x	x	x		
Postpartum Follow-up			x	x	x	x	x	x		
Data QA/Cleaning		x	x	x	x	x	x	x	x	
Primary & Secondary Analyses								x	x	x
Publication & Presentations								x	x	x
Study Meetings	x	x	x	x	x	x	x	x	x	x

## GDM Diagnostic Criteria

## GDM Study Overview

Table 1: Overview of Data Collection and study visit

Description of Assessments	Phone Screen 18-24 weeks	Visit 1: Baseline 24-28 weeks	Visit 2: 25-32 weeks	Delivery	6-8 weeks post-partum	3 Months	6 Months	9 Months	Visit 3: 1 y post-partum	Physician Input: ongoing
Screen for Eligibility	X									
Consent										
• Verbal	X									
• Written		X								
Questionnaires										
• Pt views			X		X				X	X
• Physician views					X					X
• Health			X						X	
• Dietary recall									X	X
• Infant feeding			X	X		X	X	X		
• Health Outcomes						X	X	X		
Lab Tests										
• 50 g GCT		X								
• 2 hr or 3 hr OGTT			X						X	
• Clinical and cytokine			X						X	
• Cord Blood				X						
• Urine pregnancy									X	
Anthropometric:										
• Weight		X							X	
• Height		X							X	
• Caliper measures									X	
• Circumferences									X	
PEAPOD Assessment				X						
EHR Data Abstraction										
• Delivery Data				X						
• Diabetes rescreening rates					X				X	
• Medical and surgical history, labs and testing		X		X a	X a				X a	

## **Recruitment Plan**

The GDM2 Study's goal is to recruit 920 pregnant women between 18w0d and 28w0d gestation. Participants will be women undergoing care in the following clinics:

- Resident Outpatient Clinic – Red Unit (public)
- Resident Outpatient Clinic – Blue Unit (public)
- Resident Outpatient Clinic – Orange Unit (Midwives; public)
- Resident Outpatient Clinic – Orange Unit (public)
- Resident Outpatient Clinic – Yellow Unit (public)
- Resident Outpatient Clinic – Pink Unit (public)
- Resident Outpatient Clinic – Tan Unit (PAC; public)
- Resident Outpatient Clinic – Tan Unit (Midwives; public)
- OB/GYN Associates of Pittsburgh (private)
- Maternal-Fetal Medicine (private)
- University NIA OB/GYN Associates (private)
- Midwives at Magee (private)
- WomanCare Associates (3 clinics within MWH; private)
- Wiesenfeld-Updike (private)

We will use various recruitment methods, including physician letters, flyers, brochures, the Epic Best Practice Alert (BPA), the Pitt+Me research registry, the MWH electronic message boards, newsletters such as “UPMC Extra”, and the University of Pittsburgh’s “Read Green”, and TrialSpark, which uses social media as a recruitment tool. Recruitment materials can be found in [Appendix A](#).

### **Magee-Womens Hospital Clinic Recruitment**

#### *Provider and Staff Orientation*

Before active recruitment begins, provider and staff orientation meetings will be held at the selected obstetrical clinics located at MWH. Drs. [name] and [name] will present the protocol, explain study procedures, and ask for preferences regarding study participating and relaying results. These orientation meetings will acquaint providers and their staff with the project and will help to promote patient referrals to the study. Study staff will maintain ongoing contact with the selected clinics to keep providers and staff informed on study progress and to address any site-specific issues or problems with study implementation.

### *In-Clinic Recruitment*

Women undergoing care in the selected obstetrical clinics will be considered for enrollment in this study. Contact cards and drop boxes will be placed in several of the selected clinics' waiting rooms. Study staff will collect these cards once a week and follow-up with potential participants by telephone or email.

Potential participants can be pre-screened (informing the individual about the study and collecting their contact information) or screened (informing the individual about the study and completing the 11-item screening questionnaire) during their regular OB visits. If study staff is on-site, clinic staff or providers can ask potential participants if they would be willing to hear about the study. With the patient's permission, study staff will present the study using the same script that is used for telephone screening. If the patient is interested, they can then be screened using the 11-item screening questionnaire. (See [Appendix B.](#)) Face-to-face screening will take place in a private area such as an exam room or consult office.

### *Epic Best Practice Alert*

A Best Practice Alert (BPA) within the Epic outpatient record will alert providers when a potential participant is within the gestational age eligibility window and prompt them to ask if the potential participant is interested in participating in the study. If a potential participant is agreeable the BPA will be used to notify study staff, who will then contact them by phone to describe the study and screen them further for eligibility.

### **Additional Recruitment Methods**

Posters, flyers, and brochures (see [Appendix A](#)) will be placed in exam rooms, waiting rooms, and restrooms within clinic offices, and on approved bulletin boards throughout MWH for patient self-referral, and to remind clinic staff to refer potential participants to the study. Flyers and brochures will also be distributed in public areas throughout the Pittsburgh metropolitan area, such as the WIC office in downtown. Letters and brochures are put into the new OB packets that are given to patients in the clinics.

A "featured research study" description will be including in the "UPMC Extra" email newsletter that is sent to all UPMC employees, for interested women to self-refer to the study. Similarly, the University of Pittsburgh's "Read Green" email newsletter will also be used to recruit potentially interested employees. A description of the study will be posted on CTSI's Pitt+Me research

registry website for women to self-refer. Pitt+Me also distributes emails that will advertise the study to women who may be eligible based upon demographics and/or participant-chosen health areas of interest. Pitt+Me advertises over multiple social media avenues such as Twitter and Facebook.

Another recruitment avenue through CTSI that will be utilized is the Pediatric PittNet. PittNet is a practice-based research network that works collaboratively with University of Pittsburgh researchers and pediatric primary care practices. Study advertisements will be on their website and message boards located in pediatric offices. PittNet also rotates featured research studies each month, and this study will be added to the rotation to be featured on their website and newsletter.

Digital message boards throughout the UPMC Health System will be used to advertise the study. TV screens at the following UPMC hospitals will display a PowerPoint slide with a brief description of the study and contact information for interested women.

- UPMC Magee-Womens Hospital
- UPMC Children's Hospital of Pittsburgh
- UPMC East
- UPMC McKeesport
- UPMC Mercy
- UPMC Passavant
- UPMC Presbyterian
- UPMC Shadyside
- UPMC St. Margaret

TrialSpark will be used as a recruitment source for the study. It uses advertisements on social media platforms such as Facebook and Twitter to direct interested women to fill out a pre-screening form through TrialSpark's unique GDM2 Study landing page (see [Appendix A](#)).

## Screening Procedures

### **Eligibility Criteria**

Study staff will contact patients expressing an interest in study participation in-person or by telephone to determine eligibility. A pre-screening interview will be conducted, where the study will be explained in detail using an IRB-approved script (see [Appendix A](#)).

After explaining the study in detail, study staff will ask for verbal consent to administer the screening questionnaire (see [Appendix B](#)). Screening information will be entered directly into the study database, which will automatically determine eligibility based on the study's inclusion and exclusion criteria as follows:

Participants are **eligible** to participate if they meet the following criteria:

- Between the ages of 18-45 years of age
- A singleton pregnancy at the time of screening between the gestational ages of 18w0d-28w6d

Participants are **ineligible** to participate if they meet any of the following criteria:

- Pre-existing Type 1 or Type 2 Diabetes Mellitus
- Diabetes diagnosed <24 weeks gestational age
- Multiple gestations (e.g., twins)
- Hypertension, requiring medication
- Corticosteroid (IM, IV, or oral) use in the past 30 days
- Major fetal congenital anomaly
- Anticipated pre-term delivery because of maternal or fetal indications before 34 weeks gestational age
- Inability to complete the glucose testing before 32 weeks gestational age
- Advanced HIV
- Severe liver disease (as indicated by elevated transaminase [AST] and/or alanine transaminase [ALT] values)
- Dumping syndrome as a result of gastric bypass surgery, or other illness/surgery, that preclude them from drinking the gluco solution

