### **Documentation of Study Participation in the EMR or Fax**

Once a participant has been screened and agreed to participate in the study, study staff will alert a participant's provider of study participation via fax or the participant's Epic EMR. (See [Appendix G](#) for Epic documentation templates.) This is important so that the provider does not order a 50 g GCT outside of the study, which would unblind the provider and participant, making the participant ineligible to participate. Different providers prefer different modes of notification. Desired mode of notification will be addressed a provider/staff orientation meetings and made known to study staff. If a participant's provider prefers fax or cannot be contacted through the Epic EMR system, a completed GDM2 cover sheet and study participation letter (see [Appendix A](#)) are to be faxed, and the originals and fax confirmation sheet retained.

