### **Visit 1: 50 g GCT**

#### **Preparation for Visit 1 (50 g GCT)**

Once the participant is screened and determined to be eligible, study staff will:

- Schedule the participant for their Visit 1 (50 g GCT) between 24w0d and 28w6d
- Schedule Visit 1 in the CTSI portal and the GDM2 shared team Outlook calendar
- Prepare paperwork for the visit, to include:
  - Informed consent document
  - CTRC Visit cover sheet
  - Research requisition form for the UPMC Clinical Laboratory Building (CLB), to be sent with the study specimen
- Send the participant an appointment reminder and directions to the MWH CTRC via mail or email (see [Appendix A](#))
- Call, text, or email the participant with an appointment confirmation reminder the day before their scheduled visit
  - Participants should be reminded that they do not have to fast, and that their visit will take approximately 1 hour and 30 minutes

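### The automatic exclusion list covers diabetes diagnosed in this pregnancy only before 24 weeks and omits the protocol's own outside-testing rule, although screening and Visit 1 run to 28w6d

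*Protocol*

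**What the plan says.** The Eligibility Criteria section has the study database "automatically determine eligibility" from the inclusion and exclusion criteria printed there. Two items concern diabetes: "Pre-existing Type 1 or Type 2 Diabetes Mellitus" and "Diabetes diagnosed <24 weeks gestational age". The same section admits "A singleton pregnancy at the time of screening between the gestational ages of 18w0d-28w6d", and Documentation of Eligibility repeats the 28w6d limit. For the first study test, staff are told to "Schedule the participant for their Visit 1 (50 g GCT) between 24w0d and 28w6d".

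A further eligibility rule stands elsewhere. Documentation of Study Participation in the EMR or Fax has staff alert the provider once a woman has been screened and has agreed to take part, so that no 50 g GCT is ordered outside the study, "which would unblind the provider and participant, making the participant ineligible to participate". The exclusion list has no such item.

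The screening window is stated in three ways. Table 1 has "Phone Screen 18-24 weeks", the Recruitment Plan aims to "recruit 920 pregnant women between 18w0d and 28w0d gestation", and the eligibility sections run to 28w6d.

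**The concern.** The diagnosis exclusion ends on the day the study's testing window opens. For a woman who contacts the study late, the weeks in which her own provider might test her are the weeks the list does not cover. The protocol recognises the threat, because it warns providers off their own GCT, but the rule it states is not among the criteria the database applies.

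The trial compares two diagnostic strategies. The Blinding section has providers unaware of which test was done and of the values, and treating according to the diagnosis the study reports. A provider who already holds a clinical result or diagnosis is not in that position. The woman may already be under treatment when the study OGTT is done, and her management follows the earlier result and not the allocated strategy, which dilutes the contrast between arms. The study report may also disagree with her chart. In Arm B the GDM criteria require a study GCT of at least 130 mg/dL, so with a lower value she would generally be reported negative even if a diagnosis is on record. The protocol does not say how two such reports are to be reconciled.

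**Working it through.** The plan gives no figure to reproduce here. The check is a day count and a comparison of sections.

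**Day count (inclusive).**
- Screening window: 18w0d is day 18 × 7 = 126 and 28w6d is day 28 × 7 + 6 = 202, so 202 − 126 + 1 = 77 days.
- Visit 1 window: 24w0d is day 24 × 7 = 168, so 202 − 168 + 1 = 35 days.
- The diagnosis item fails to reach 35 / 77 = 45% of the screening days, and all 35 days of the Visit 1 window.

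**Following a late contact through the protocol.** Take a woman first contacted at 26 weeks.

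| Step | Section | Outside 50 g GCT at 25 weeks | Diagnosed at 25 weeks by another route (such as a direct OGTT) |
|---|---|---|---|
| Automatic check | Eligibility Criteria | No listed item applies | No listed item applies |
| Outside-testing rule | Documentation of Study Participation | Ineligible, if staff learn of it | Not covered; the rule names only the 50 g GCT |
| EMR review | Documentation of Eligibility; Screening Time Point Forms | May reveal it | May reveal it, but no criterion makes her ineligible |
| Visit 1 | Informed Consent; Visit 1 Forms | No check for outside testing described | No check for an earlier diagnosis described |
| Randomisation | Visit 1 Results; Randomization Procedures | Study GCT below 200 mg/dL, baseline measures complete | The same |
| Later removal | Study Withdrawal and Termination | Possible if she is recognised as ineligible | The exclusion-criteria ground does not apply, as she meets none |

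**Timing of the EMR review.** It belongs to the screening time point. Screening can be at 18w0d and Visit 1 as late as 28w6d, a gap of up to 202 − 126 = 76 days, and no repeat look is described. The look-up that Documentation of Eligibility spells out concerns dating only (EDC or ultrasound), although the Recruitment Form entry says the review also serves to confirm eligibility.

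**The case against.** The strongest reply is that the protocol as a whole already bars the commonest case. It describes the usual clinical diagnosis as starting from a 50 g GCT, and a GCT done outside the study makes a woman ineligible. Provider notification is forward-looking, but the reason given for ineligibility, that provider and participant are unblinded, applies equally to a GCT done before contact. There are also backstops: the EMR review, the option to hold a screening survey open until an investigator is consulted, removal of participants who meet exclusion criteria, and a deviation form that names enrolment of an ineligible participant. The 24-week cut may be deliberate, excluding diabetes found before the study's own testing window and leaving later tests to the outside-testing rule. Table 1 is weak evidence of intent, since it still lists the PEAPOD assessment that the table of changes records as removed.

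Much of this stands. A reader might infer that any woman already tested or diagnosed at 24w0d to 28w6d goes on to be randomised. The document does not support that: with an outside 50 g GCT she is ineligible once staff know, and the chart review gives them a chance to know. A reader might also take 45% as a share of participants. It is a share of calendar days, and any percentage of the 920 recruits put forward as affected would be a guess.

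The reply does not close the gap. The backstops work through the criteria, and the criteria contain neither the outside-testing rule nor a diagnosis at 24 weeks or later. If the two rules were meant to work together, they still leave out a diagnosis made without a 50 g GCT.

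**Conclusion.** The point holds as an inconsistency between two eligibility statements, with one real hole. For a woman with an outside 50 g GCT, the defect is that a stated rule is missing from the list the database applies, so her exclusion depends on staff finding out. For a woman diagnosed at 24 weeks or later by another route, no text excludes her and she can be randomised.

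The extent in time is 35 of 77 screening days and the whole Visit 1 window. The number of women affected, and so any loss of contrast between arms, cannot be derived from the document. The screening questionnaire is in an appendix that is not shown and may ask about outside testing; the conclusion assumes that the automatic decision follows the printed criteria, as the section says. The point deserves correction because it touches blinding and the arm contrast and is cheap to repair. It does not show that the comparison is invalid.

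**What to change.** 1. Extend the listed exclusion to diabetes or GDM diagnosed at any time in this pregnancy before Visit 1.
2. Carry the outside-testing rule into the exclusion list and the screening survey, so that a 50 g GCT done outside the study fails the automatic check. The rule carries no gestational-age limit; adding one would narrow it, so none should be added.
3. Have staff check both items again in the EMR at Visit 1, before the glucose drink is given, under the access already agreed at screening.
4. Align the screening windows in Table 1 (18-24 weeks), the Recruitment Plan (28w0d) and the eligibility sections (28w6d).

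The cost is a change to two eligibility items and the matching survey fields, one short chart look-up per participant, and the loss of a few women who should not be randomised.

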### *Hypertension and Corticosteroid Medications*

For hypertension, treatment with low-dose/baby aspirin (LDASA/BASA) is acceptable. If a participant was on hypertension medication before pregnancy but was discontinued in their first trimester, they are eligible to participate.

A participant is still eligible to enter the study if they can complete a 30-day washout period post-corticosteroid use, before completing the Visit 1 appointment within their eligibility window. If it is discovered that a participant was on corticosteroid medications within 30 days of Visit 1, they will not be withdrawn, but the medication use should be documented in the Concomitant Medication Form in the database.

Once a participant has been enrolled in the study, if they start a corticosteroid medication, study staff should try to schedule Visit 2 (or Visit 3) after a 7-day washout period has been completed. If the participant will be out of window, then staff should still schedule the study participant to complete their visit in window. At that visit, staff should document the medication use in the Concomitant Medication Form.

Hypertension medications	Hypertension medications	Corticosteroids (IV, IM, oral)
Amlodipine	Labetalol	Betamethasone
Atenolol	Lisinopril	Budesonide
Bisoprolol	Losartan	Cortisone
Carvedilol	Methyldopa	Dexamethasone
Diazide	Metoprolol	Hydrocortisone
Diltiazem	Nadolol	Methylprednisolone
Enalapril	Nifedipine	Prednisolone
Furosemide	Triamterine	Prednisone
Hydrochlorothiazide (HCTZ)	Valsartan	

### *Documentation of Eligibility*

If study staff have questions related to a potential participant's eligibility, the option to keep the screening survey open is available in the study database, until the PI or Site PI can be consulted.

Once primary eligibility has been established, study staff will complete a recruitment form, collect the participant's contact information, and verify their gestational age (GA). At this time, the participant will be asked to give their verbal consent for study staff to enter the participant's electronic medical record (EMR) in Epic. After obtaining verbal consent, study staff will verify

gestational age in the participant's EMR, by checking the estimated date of confinement (EDC) and/or dating by ultrasound.

GA will be calculated by the database by the weeks/days from date of the screening time point to the EDC entered into the database. If GA is between 18w0d and 28w6d, the participant is eligible to undergo their 50-gram Glucose Challenge Test (GCT) between 24w0d-28w6d through the GDM2 Study. If the participant's GA is <18w0d, the participant will be placed into a "pending" category and will be re-contacted once they reach 18w0d. NOTE: If a potential participant is <14 weeks upon initial contact, they must be re-screened at 18w0d. Participants whose GA has exceeded 28w6d are ineligible and will be moved to the ineligible category within the database.

### **Documentation of Study Participation in the EMR or Fax**

Once a participant has been screened and agreed to participate in the study, study staff will alert a participant's provider of study participation via fax or the participant's Epic EMR. (See [Appendix G](#) for Epic documentation templates.) This is important so that the provider does not order a 50 g GCT outside of the study, which would unblind the provider and participant, making the participant ineligible to participate. Different providers prefer different modes of notification. Desired mode of notification will be addressed a provider/staff orientation meetings and made known to study staff. If a participant's provider prefers fax or cannot be contacted through the Epic EMR system, a completed GDM2 cover sheet and study participation letter (see [Appendix A](#)) are to be faxed, and the originals and fax confirmation sheet retained.

